6.2.11. Visit 11 (Day 169) (Clinic and Radiology Visit)

The procedures outlined in Table 6-11 will be performed at Visit 11 (Day 169 [±3 days]).

Table 6-11. Procedures and Assessments at Visit 11 (Day 169)

Assessment or Procedure	Explanation
Pre-Visit Tumor Assessment	
Radiology assessment	CT or MRI imaging of neck, chest, abdomen, and pelvis within 1 week prior to the visit; the assessment should be done even if study drug has been interrupted.
Pre-Therapy Procedures an	nd Assessments
FACT-Leu	HRQL instrument (Appendix 2) to be administered before any other procedures are performed and before any study-related information is communicated to the subject
EQ-5D	Health utility instrument (Appendix 4) to be administered after FACT-Leu but before any other procedures are performed and before any study-related information is communicated to the subject
Adverse events	Recording of adverse events occurring since Visit 10
Concomitant medications	Recording of concomitant medication used since Visit 10
Study drug return/accounting	Counting returned study drug. Recording of the date and actual clock time of the last prior subject self-administration of study drug (should be the prior evening dose)
Performance status	Using Karnofsky performance status criteria (see Appendix 3)
Oxygen saturation	To be assessed by pulse oximetry while subject is breathing room air
Physical examination	Including weight, evidence of palpable lymphadenopathy, hepatomegaly, and/or splenomegaly
Urine β-HCG dipstick	For women of child-bearing potential only
Hematology	Including hematocrit, hemoglobin, erythrocyte count; absolute counts of leukocytes, neutrophils, lymphocytes, monocytes, eosinophils, basophils, platelet count
Serum chemistry	Including sodium, potassium, chloride, glucose, urea, creatinine, calcium, phosphorus, total protein, albumin, ALT, AST, ALP, GGT, total bilirubin, LDH, uric acid, cholesterol, triglycerides
Circulating cells	Including cells for analysis of PI3K/AKT/mTOR pathway activation and quantitation of absolute number of CD4+, CD5+, CD8+, CD16/CD56+, CD19+, and CD+20 cells by flow cytometry
Biomarkers	Collection of plasma and serum for evaluation of circulating chemokines and cytokines
Serum Igs	Including quantitative levels of IgA, IgE, IgG, IgM
Bone marrow biopsy and aspirate	To be performed post-baseline to confirm response category in subjects with potential CR by radiological assessments. If the subject does not otherwise meet criteria for CR, it is not necessary to obtain a follow-up bone marrow biopsy/aspirate to establish CR.
Idelalisib pharmacokinetics	Pre-dose collection of plasma sample for idelalisib pharmacokinetics (with recording of the date and actual clock time of the date and actual clock time of blood collection)
IWRS access	Access of IWRS to obtain study drug blister card numbers

Assessment or Procedure	Explanation
Study Therapy Administrat	tion
Study drug administration	Dose of study drug to be administered to the subject (with recording of the date and actual clock time of the study drug administration)
Post-Therapy Procedures a	nd Assessments
Idelalisib pharmacokinetics	Post-dose collection of plasma sample for idelalisib pharmacokinetics at 1.5 hours ± 15 mins after study drug administration (with recording of the date and actual clock time of blood collection)
Study drug dispensing	Dispensing of 12-week supply of study drug to the subject with instructions for self-administration at home.

Abbreviations: ALP=alkaline phosphatase, ALT=alanine aminotransferase, AST=aspartate aminotransferase, CR=complete response, CT=computed tomography, EQ-5D=EuroQoL Five-Dimension, FACT-Leu=Functional Assessment of Cancer Therapy-Leukemia, GGT=gamma-glutamyltransferase, HRQL=health-related quality of life, Ig=immunoglobulin, LDH=lactate dehydrogenase, MRI=magnetic resonance imaging

6.2.12. Visit 12 (Day 211) (Clinic Visit)

The procedures outlined in Table 6-12 will be performed at Visit 12 (Day 211 [±3 days]).

Table 6-12. Procedures and Assessments at Visit 12 (Day 211)

Assessment or Procedure	Explanation
FACT-Leu	HRQL instrument (Appendix 2) to be administered before any other procedures are performed and before any study-related information is communicated to the subject
EQ-5D	Health utility instrument (Appendix 4) to be administered after FACT-Leu but before any other procedures are performed and before any study-related information is communicated to the subject
Adverse events	Recording of adverse events occurring since Visit 11
Concomitant medications	Recording of concomitant medication used since Visit 11
Performance status	Using Karnofsky performance status criteria (see Appendix 3)
Oxygen saturation	To be assessed by pulse oximetry while subject is breathing room air
Physical examination	Including weight, evidence of palpable lymphadenopathy, hepatomegaly, and/or splenomegaly
Urine β-HCG dipstick	For women of child-bearing potential only
Hematology	Including hematocrit, hemoglobin, erythrocyte count; absolute counts of leukocytes, neutrophils, lymphocytes, monocytes, eosinophils, basophils, platelet count
Serum chemistry	Including sodium, potassium, chloride, glucose, urea, creatinine, calcium, phosphorus, total protein, albumin, ALT, AST, ALP, GGT, total bilirubin, LDH, uric acid, cholesterol, triglycerides
Circulating cells	Including cells for analysis of PI3K/AKT/mTOR pathway activation and quantitation of absolute number of CD4+, CD5+, CD8+, CD16/CD56+, CD19+, and CD+20 cells by flow cytometry
Biomarkers	Collection of plasma and serum for evaluation of circulating chemokines and cytokines
Serum Igs	Including quantitative levels of IgA, IgE, IgG, and IgM
IWRS access	Access of IWRS to document subject visit
Study drug administration	Subject to continue with study drug as prescribed.
Scheduling of Visit 13 radiology assessment	CT or MRI imaging of neck, chest, abdomen, and pelvis to be scheduled for Visit 13.

Abbreviations: ALP=alkaline phosphatase, ALT=alanine aminotransferase, AST=aspartate aminotransferase, CT=computed tomography, EQ-5D=EuroQoL Five-Dimension, FACT-Leu=Functional Assessment of Cancer Therapy-Leukemia, GGT=gamma-glutamyltransferase, HRQL=health-related quality of life, Ig=immunoglobulin, LDH=lactate dehydrogenase, MRI=magnetic resonance imaging

6.2.13. Visit 13 (Day 253) (Clinic and Radiology Visit)

The procedures outlined in Table 6-13 will be performed at Visit 13 (Day 253 [±3 days]).

Table 6-13. Procedures and Assessments at Visit 13 (Day 253)

Assessment or Procedure	Explanation	
Pre-Visit Tumor Assessmen	Pre-Visit Tumor Assessment	
Radiology assessment	CT or MRI imaging of neck, chest, abdomen, and pelvis within 1 week prior to the visit; the assessment should be done even if study drug has been interrupted.	
During-Visit Procedures an	nd Assessments	
FACT-Leu	HRQL instrument (Appendix 2) to be administered before any other procedures are performed and before any study-related information is communicated to the subject	
EQ-5D	Health utility instrument (Appendix 4) to be administered after FACT-Leu but before any other procedures are performed and before any study-related information is communicated to the subject	
Adverse events	Recording of adverse events occurring since Visit 10	
Concomitant medications	Recording of concomitant medication used since Visit 10	
Study drug return/ accounting	Counting returned study drug.	
Performance status	Using Karnofsky performance status criteria (see Appendix 3)	
Oxygen saturation	To be assessed by pulse oximetry while subject is breathing room air	
Physical examination	Including weight, evidence of palpable lymphadenopathy, hepatomegaly, and/or splenomegaly	
Urine β-HCG dipstick	For women of child-bearing potential only	
Hematology	Including hematocrit, hemoglobin, erythrocyte count; absolute counts of leukocytes, neutrophils, lymphocytes, monocytes, eosinophils, basophils, platelet count	
Serum chemistry	Including sodium, potassium, chloride, glucose, urea, creatinine, calcium, phosphorus, total protein, albumin, ALT, AST, ALP, GGT, total bilirubin, LDH, uric acid, cholesterol, triglycerides	
Circulating cells	Including cells for analysis of PI3K/AKT/mTOR pathway activation and quantitation of absolute number of CD4+, CD5+, CD8+, CD16/CD56+, CD19+, and CD+20 cells by flow cytometry	
Biomarkers	Collection of plasma and serum for evaluation of circulating chemokines and cytokines	
Serum Igs	Including quantitative levels of IgA, IgE, IgG, and IgM	
Bone marrow biopsy and aspirate	To be performed post-baseline to confirm response category in subjects with potential CR by radiological assessments. If the subject does not otherwise meet criteria for CR, it is not necessary to obtain a follow-up bone marrow biopsy/aspirate to establish CR.	
IWRS access	Access of IWRS to obtain study drug blister card numbers	
Study drug administration	Subject to continue with study drug as prescribed.	
Study drug dispensing	Dispensing of 12-week supply of study drug to the subject with instructions for self-administration at home.	

Abbreviations: ALP=alkaline phosphatase, ALT=alanine aminotransferase, AST=aspartate aminotransferase, CR=complete response, CT=computed tomography, EQ-5D=EuroQoL Five-Dimension, FACT-Leu=Functional Assessment of Cancer Therapy-Leukemia, GGT=gamma-glutamyltransferase, HRQL=health-related quality of life, Ig=immunoglobulin, LDH=lactate dehydrogenase, MRI=magnetic resonance imaging

6.2.14. Visit 14 (Day 295) (Clinic Visit)

The procedures outlined in Table 6-14 will be performed at Visit 14 (Day 295 [±3 days]).

Table 6-14. Procedures and Assessments at Visit 14 (Day 295)

Assessment or Procedure	Explanation
FACT-Leu	HRQL instrument (Appendix 2) to be administered before any other procedures are performed and before any study-related information is communicated to the subject
EQ-5D	Health utility instrument (Appendix 4) to be administered after FACT-Leu but before any other procedures are performed and before any study-related information is communicated to the subject
Adverse events	Recording of adverse events occurring since Visit 10
Concomitant medications	Recording of concomitant medication used since Visit 10
Performance status	Using Karnofsky performance status criteria (see Appendix 3)
Oxygen saturation	To be assessed by pulse oximetry while subject is breathing room air
Physical examination	Including weight, evidence of palpable lymphadenopathy, hepatomegaly, and/or splenomegaly
Urine β-HCG dipstick	For women of child-bearing potential only
Hematology	Including hematocrit, hemoglobin, erythrocyte count; absolute counts of leukocytes, neutrophils, lymphocytes, monocytes, eosinophils, basophils, platelet count
Serum chemistry	Including sodium, potassium, chloride, glucose, urea, creatinine, calcium, phosphorus, total protein, albumin, ALT, AST, ALP, GGT, total bilirubin, LDH, uric acid, cholesterol, triglycerides
Circulating cells	Including cells for analysis of PI3K/AKT/mTOR pathway activation and quantitation of absolute number of CD4+, CD5+, CD8+, CD16/CD56+, CD19+, and CD+20 cells by flow cytometry
Biomarkers	Collection of plasma and serum for evaluation of circulating chemokines and cytokines
Serum Igs	Including quantitative levels of IgA, IgE, IgG, and IgM
IWRS access	Access of IWRS to document subject visit
Study drug administration	Subject to continue with study drug as prescribed.
Scheduling of Visit 15 radiology assessment	CT or MRI imaging of neck, chest, abdomen, and pelvis to be scheduled for Visit 15.

Abbreviations: ALP=alkaline phosphatase, ALT=alanine aminotransferase, AST=aspartate aminotransferase, CT=computed tomography, EQ-5D=EuroQoL Five-Dimension, FACT-Leu=Functional Assessment of Cancer Therapy-Leukemia, GGT=gamma-glutamyltransferase, HRQL=health-related quality of life, Ig=immunoglobulin, LDH=lactate dehydrogenase, MRI=magnetic resonance imaging

6.2.15. Visit 15 and Subsequent Visits (Day 337 and Every 12 Weeks) (Clinic and Radiology Visits)

The procedures outlined in Table 6-15 will be performed at Visit 15 (Day 337 [±3 days]) and every 12 weeks thereafter [±7 Days]).

Table 6-15. Procedures and Assessments at Visit 15 and Subsequent Visits (Day 337 and Every 12 Weeks)

Assessment or Procedure	Explanation	
Pre-Visit Tumor Assessmen	Pre-Visit Tumor Assessment	
Radiology assessment ^a	CT or MRI imaging of neck, chest, abdomen, and pelvis within 1 week prior to the visit; the assessment should be done even if study drug has been interrupted.	
During-Visit Procedures an	nd Assessments	
FACT-Leu	HRQL instrument (Appendix 2) to be administered before any other procedures are performed and before any study-related information is communicated to the subject	
EQ-5D	Health utility instrument (Appendix 4) to be administered after FACT-Leu but before any other procedures are performed and before any study-related information is communicated to the subject	
Adverse events	Recording of adverse events occurring since prior visit	
Concomitant medications	Recording of concomitant medication used since prior visit	
Study drug return/accounting	Counting returned study drug.	
Performance status	Using Karnofsky performance status criteria (see Appendix 3)	
Oxygen saturation	To be assessed by pulse oximetry while subject is breathing room air	
Physical examination	Including weight, evidence of palpable lymphadenopathy, hepatomegaly, and/or splenomegaly	
Urine β-HCG dipstick	For women of child-bearing potential only	
Hematology	Including hematocrit, hemoglobin, erythrocyte count; absolute counts of leukocytes, neutrophils, lymphocytes, monocytes, eosinophils, basophils, platelet count	
Serum chemistry	Including sodium, potassium, chloride, glucose, urea, creatinine, calcium, phosphorus, total protein, albumin, ALT, AST, ALP, GGT, total bilirubin, LDH, uric acid, cholesterol, triglycerides	
CMV viral load	CMV viral load testing approximately every 4 weeks throughout the course of idelalisib treatment	
Circulating cells	Including cells for analysis of PI3K/AKT/mTOR pathway activation and quantitation of absolute number of CD4+, CD5+, CD8+, CD16/CD56+, CD19+, and CD+20 cells by flow cytometry	
Immune monitoring	Lymphocyte subset panel using flow cytometry (immunophenotyping), serum CH50 level	
Biomarkers	Collection of plasma and serum for evaluation of circulating chemokines and cytokines	

Assessment or Procedure	Explanation
Serum Igs	Including quantitative levels of IgA, IgE, IgG, and IgM
Bone marrow biopsy and aspirate	To be performed post-baseline to confirm response category in subjects with potential CR by radiological assessments. If the subject does not otherwise meet criteria for CR, it is not necessary to obtain a follow-up bone marrow biopsy/aspirate to establish CR.
IWRS access	Access of IWRS to obtain study drug blister card numbers
Study drug administration	Subject to continue with study drug as prescribed.
Study drug dispensing	Dispensing of 12-week supply of study drug to the subject with instructions for self-administration at home
PJP prophylaxis	Subjects must receive trimethoprim-sulfamethoxazole or other established prophylaxis for PJP throughout the course of idelalisib treatment. Subjects must permanently discontinue idelalisib upon diagnosis of PJP.
Scheduling of next visit radiology assessmenta	CT or MRI imaging of neck, chest, abdomen, and pelvis to be scheduled for next clinic visit (every 12 weeks).

a As of Amendment 9, Version 10, CT/MRI assessments will no longer be performed at the every 12 week scheduled visits, and will only be performed at the time of clinically-suspected disease progression or at study discontinuation.
 Abbreviations: ALP=alkaline phosphatase, ALT=alanine aminotransferase, AST=aspartate aminotransferase,
 CMV=cytomegalovirus, CR=complete response, CT=computed tomography, EQ-5D=EuroQoL Five-Dimension,
 FACT-Leu=Functional Assessment of Cancer Therapy-Leukemia, GGT=gamma-glutamyltransferase, HRQL=health-related quality of life, Ig=immunoglobulin, LDH=lactate dehydrogenase, MRI=magnetic resonance imaging, PJP= Pneumocystis jirovecii pneumonia

6.2.16. End-of-Study Visit (Clinic Visit)

At the time of discontinuation from the study, the subject should have the procedures and assessments performed as documented in Table 6-16. An end-of-study CT/MRI tumor assessment should be performed unless the subject already has radiographic confirmation of definitive disease progression or a CT/MRI has been performed within 4 weeks prior to the end-of-study visit.

Table 6-16. Procedures and Assessments at End-of-Study Visit

Assessment or Procedure	Explanation
Radiology assessment ^a	CT or MRI imaging of neck, chest, abdomen, and pelvis
FACT-Leu	HRQL instrument (Appendix 2) to be administered before any other procedures are performed
EQ-5D	Health utility instrument (Appendix 4) to be administered after FACT-Leu but before any other procedures are performed
Adverse events	Recording of adverse events occurring since prior visit; if a clinically significant adverse event or abnormal result is observed that is not resolved by the end-of-treatment visit, repeat evaluations should be performed to document resolution or stabilization of the abnormality
Concomitant medications	Recording of concomitant medication used since prior visit
Study drug return/accounting	Counting returned study drug.
Performance status	Using Karnofsky performance status criteria (see Appendix 3)
Oxygen saturation	To be assessed by pulse oximetry while subject is breathing room air
Physical examination	Including weight, evidence of palpable lymphadenopathy, hepatomegaly, and/or splenomegaly
Serum β-HCG	Women of childbearing potential only
CLL peripheral blood evaluation	Including FISH for chromosome 11q deletion, 13q deletion, 17p deletion and 12 trisomy; DNA mutational analysis for p53, IgHV (including IgHV3-21), and other genes of interest in CLL (eg, Notch); flow cytometry for CD5, CD10, CD11c, CD19, CD20, CD23, CD38, CD45, kappa and lambda light chains, and ZAP-70; cytology for karyotyping
CLL serology	Serum β2 microglobulin
PPD	PPD
Hematology	Including hematocrit, hemoglobin, erythrocyte count; absolute counts of leukocytes, neutrophils, lymphocytes, monocytes, eosinophils, basophils, platelet count
Serum chemistry	Including sodium, potassium, chloride, glucose, urea, creatinine, calcium, phosphorus, total protein, albumin, ALT, AST, ALP, GGT, total bilirubin, LDH, uric acid, cholesterol, triglycerides

Assessment or Procedure	Explanation
Circulating cells	Including cells for analysis of PI3K/AKT/mTOR pathway activation and quantitation of absolute number of CD4+, CD5+, CD8+, CD16/CD56+, CD19+, and CD+20 cells by flow cytometry
Immune monitoring	Lymphocyte subset panel using flow cytometry (immunophenotyping), serum CH50 level
Biomarkers	Collection of plasma and serum for evaluation of circulating chemokines and cytokines
Serum Igs	Including quantitative levels of IgA, IgE, IgG, and IgM
PJP prophylaxis	Subjects must receive trimethoprim-sulfamethoxazole or other established prophylaxis for PJP after completion of idelalisib treatment until the CD4+ T-cell count is > 200 cells/mcL, at which point PJP prophylaxis may be discontinued.
IWRS	Access IWRS to document that subject has permanently discontinued study therapy and to indicate whether subject agrees to continue to undergo long-term follow-up

a An end-of-study CT/MRI tumor assessment should be performed unless the subject has had a CT/MRI assessment ≤4 weeks prior to end-of-study discontinuation.

Abbreviations: β-HCG=beta human chorionic gonadotropin, ALP=alkaline phosphatase, ALT=alanine aminotransferase, AST=aspartate aminotransferase, CLL=chronic lymphocytic leukemia, CT=computed tomography, FISH= fluorescence in-situ hybridization, GGT=gamma-glutamyltransferase, IgHV=immunoglobulin heavy-chain variable-region, IWRS=interactive web response system, LDH=lactate dehydrogenase, MRI=magnetic resonance imaging, PJP= *Pneumocystis jirovecii pneumonia*, RNA=ribonucleic acid, ZAP-70=zeta-associated protein 70

6.2.17. 30 Day and Long-Term Follow-up

A 30 Day follow-up visit will be performed 30 (+ 5) days following the end-of-study visit; however, it may be waived for subjects who have permanently discontinued study drug and have had a study visit >30 days after the last dose of study drug.

Long-term, follow-up will be requested of all subjects who withdraw from study for any reason.

The long-term follow-up for survival will be conducted at ~6-month intervals for 5 years, starting at the end-of-study visit. Information may be gathered during a routine clinic visit or other contact with the subject, or via telephone. Information gathered will include medical status, anti-tumor treatments, secondary malignancies, and survival.

[figure not shown]

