5.4.5. Infectious Events

Patients with lymphoid cancers receiving idelalisib have developed serious and fatal infections during therapy. Opportunistic infections, most notably Pneumocystis jirovecii pneumonia (PJP) and CMV infection, have most frequently occurred within the first 6 months of treatment with idelalisib and are increased in the context of concurrent myelosuppressive therapy such as bendamustine.

Subjects must receive trimethoprim-sulfamethoxazole or other established prophylaxis for PJP throughout the course of idelalisib treatment, and must continue for 2 to 6 months after the last dose of idelalisib. Prophylaxis must continue until the CD4+ T-cell count is documented to be >200 cells/mcL after idelalisib treatment ends. Subjects must permanently discontinue idelalisib upon diagnosis of PJP.

CMV surveillance for active disease (quantitative PCR or PP65 antigen) must be conducted approximately every 4 weeks throughout the course of idelalisib treatment. CMV viral load testing should be performed from the same specimen type whenever possible and caution should be exercised when comparing CMV viral load results across different testing centers. If unequivocal clinical or laboratory evidence of CMV infection is present, the subject must interrupt idelalisib treatment and undergo effective antiviral treatment according to established clinical guidelines. If the benefits of resuming idelalisib are judged to outweigh the risks, consideration should be given to administering pre-emptive CMV therapy.

Serious bacterial, fungal, and new or reactivated viral infections have occurred during and for ~1 year following rituximab-based therapy {Gea-Banacloche 2010}. New or reactivated viral infections in patients receiving rituximab have included CMV, herpes simplex virus, parvovirus B19, varicella zoster virus, West Nile virus, HBV (see Section 5.4.3) and HCV.

In high-risk subjects (history of recurrent infection, allogeneic transplant, treatment with alemtuzumab, hypogammaglobulinemia) other infection prophylaxis should be considered per consensus guidelines. Administration of intravenous immunoglobulin is permitted per standard institutional practice {Raanani 2009}. For subjects who develop an infection, appropriate medical therapy should be instituted in a timely manner.

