5.8. Discontinuation of Study Drug

All study participants may receive study drug indefinitely; however:

- Any subject has the right to discontinue study drug at any time.
- Any subject who has objective evidence based on IRC review of definitive CLL progression will discontinue study drug.

- Any subject unable to tolerate a second rechallenge with protocol-described, dose-modified idelalisib at Dose Level –1 (see Section 5.2) should discontinue study drug.
- Any subject who becomes pregnant or begins breastfeeding should discontinue study drug.
- Any subject who becomes significantly noncompliant with study drug administration, study procedures, or study requirements should discontinue study drug.
- Any subject for whom the blind is intentionally broken by the subject or the study site should discontinue study drug (only applicable to the blinded portion of the study).
- The investigator, in consultation with the Gilead Sciences medical monitor, may discontinue study drug, if, it is not in the subject's best interest to continue.
- If allowed by local regulations, Gilead Sciences may transition subjects from study drug to commercial drug supply when idelalisib becomes commercially available in the country where the subject is living.
- Any subject who is diagnosed with any grade of SJS, TEN, PJP, or organizing pneumonia, or any subject diagnosed with Grade ≥2 pneumonitis should discontinue study drug.

Any subject whose benefit-risk profile is not deemed positive by the investigator should discontinue study drug.

Subjects who permanently discontinue study drug for a reason other than disease progression (as determined by the IRC) shall continue with assessments per the schedule of procedures until disease progression or until another anticancer or experimental therapy is initiated.

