5.9. Discontinuation from Study

Subject study participation will be ended due to any of the following reasons:

- Adverse event.
- Disease progression.
- Withdrawal of consent.
- Significant subject noncompliance with study drug administration, study procedures, or study requirements.
- Initiation of any additional systemic anticancer therapies (other than corticosteroids, see Section 5.6.5) including chemotherapy, radiation, antibody therapy, immunotherapy, or other experimental treatment.
- Physician's decision to remove the subject from the study.
- Pregnancy.
- The subject is lost to follow-up.

- Death.
- Discontinuation of study by the Sponsor, a Regulatory Agency, or an IRB or EC.

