- i PJP prophylaxis: subjects must receive trimethoprim-sulfamethoxazole or other established prophylaxis for PJP throughout the course of idelalisib treatment and for 2 to 6 months after the last dose of idelalisib. Subjects must permanently discontinue idelalisib upon diagnosis of PJP. Prophylaxis will continue for 2 to 6 months after the last dose of idelalisib and until the CD4+ T-cell count is documented to be >200 cells/mcL after idelalisib treatment ends.
- i CD4+ T-cell count (related to PJP prophylaxis): PJP prophylaxis will continue until the CD4+ T-cell count is documented to be >200 cells/mcL after idelalisib treatment ends.
- k As of Amendment 9, Version 10, CT/MRI assessments will no longer be performed at the every 12 week scheduled visits, and will only be performed at the time of clinically-suspected disease progression or at study discontinuation.

Abbreviations: β-HCG=beta human chorionic gonadotropin, CIRS=chronic illness rating scale, CLL=chronic lymphocytic leukemia, CMV=cytomegalovirus, CR=complete response, CT=computed tomography, EQ-5D=EuroQoL Five-Dimension, FACT-Leu=Functional Assessment of Cancer Therapy- Leukemia, HRQL= health-related quality of life, Ig=immunoglobulin, IWRS=interactive web response system, MRI= magnetic resonance imaging, PJP= *Pneumocystis jirovecii* pneumonia.

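### Table 6-16 lets sites stop PJP prophylaxis on the CD4+ count alone, omitting the 2 to 6 months after the last dose that Section 5.4.5 also requires

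*Protocol*

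**What the plan says.** Section 5.4.5 (Infectious Events) sets two mandatory conditions for prophylaxis once idelalisib stops. On time, it "must continue for 2 to 6 months after the last dose of idelalisib". On the cell count, "Prophylaxis must continue until the CD4+ T-cell count is documented to be >200 cells/mcL after idelalisib treatment ends".

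Appendix 7 footnote i joins the two: "Prophylaxis will continue for 2 to 6 months after the last dose of idelalisib and until the CD4+ T-cell count" is documented above the threshold. Footnote j, the only footnote on the End-of-Study cell of the PJP row, repeats the count condition alone: "PJP prophylaxis will continue until the CD4+ T-cell count is documented to be >200 cells/mcL after idelalisib treatment ends".

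Table 6-16 in Section 6.2.16, which lists what sites do at the End-of-Study visit, requires prophylaxis after idelalisib treatment is completed "until the CD4+ T-cell count is > 200 cells/mcL, at which point PJP prophylaxis may be discontinued". It mentions no minimum time and does not refer to Section 5.4.5.

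**The concern.** Table 6-16 is not merely silent on duration. It names the point at which prophylaxis may stop, and that point can come before the earliest one Section 5.4.5 allows. Section 5.4.5 itself reports serious and fatal infections with idelalisib and names PJP among the most notable opportunistic infections, so this is an operative safety rule.

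The conflict matters when End of Study falls at or near the last dose. That is the planned path for subjects who progress. Under Section 5.8, a subject with "definitive CLL progression will discontinue study drug". Section 5.9 lists disease progression under the heading "Subject study participation will be ended due to any of the following reasons". CD4+ cells are counted at the End-of-Study visit, so the Table 6-16 condition can be met from that sample.

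Later contacts are unlikely to reverse an early stop. Section 6.2.17 schedules a visit 30 (+5) days after End of Study and then survival follow-up about every 6 months. Appendix 7 lists only adverse events and concomitant medications at the 30-day visit, with no CD4+ count.

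**Working it through.** The plan gives no figure to reproduce. The check sets the stopping rules side by side and then measures the gap between them.

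**Step 1. The rules compared.**

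| Source | Time after last dose | CD4+ >200 cells/mcL | Permits stopping? |
|---|---|---|---|
| Section 5.4.5 | 2 to 6 months, mandatory | Yes, mandatory | Only when both are met |
| Appendix 7, footnote i | 2 to 6 months | Yes, joined by 'and' | Only when both are met |
| Appendix 7, footnote j | Not stated | Yes | No permission given |
| Table 6-16 | Not stated | Yes | Yes, on the count alone |

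Table 6-16 is the only entry that conflicts with Section 5.4.5. Footnote j is incomplete but gives no leave to stop, and the label of the PJP row in Appendix 7 also carries footnote i.

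**Step 2. The shortfall.** Let t be the months from the last dose to the point at which Table 6-16 allows stopping (CD4+ above 200). However the 2 to 6 month range is read, 2 months is the earliest stop Section 5.4.5 allows. Hence

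shortfall = max(0, 2 − t) months.

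| t (months) | 0 | 0.5 | 1 | 1.5 | 2 or more |
|---|---|---|---|---|---|
| Shortfall (months) | 2.0 | 1.5 | 1.0 | 0.5 | 0 |

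**Step 3. In days, on the protocol's contact schedule.** One month is 365.25/12 = 30.44 days, so 2 months is 60.9 days. Assume that End of Study is on the day of the last dose.

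- Stop at End of Study (day 0): 60.9 days, or 2.00 months.
- Stop at the follow-up visit, day 30: 60.9 − 30 = 30.9 days, or 1.01 months.
- Stop at the follow-up visit, day 35: 60.9 − 35 = 25.9 days, or 0.85 months.

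**Step 4. Who is not affected.** The shortfall is zero while CD4+ stays at or below 200, because both rules then require prophylaxis to continue. Under Section 5.8, subjects who stop drug for a reason other than progression "shall continue with assessments per the schedule of procedures until disease progression or until another anticancer or experimental therapy is initiated". On that schedule CD4+ is counted every 12 weeks from Visit 15 (Table 6-15). Their End-of-Study visit may fall 2 months or more after the last dose, and the time condition that Table 6-16 omits would then already be met at its minimum.

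**The case against.** The best counter-argument is that the full rule appears twice: in Section 5.4.5, and in the Appendix 7 schedule, where footnote i sits on the row label. Table 6-16 permits stopping but does not require it, so a site that follows Section 5.4.5 breaches nothing. On this view harm needs a site to overlook both other statements, and the table cell is only an abbreviation. It remains true that a careful reader can recover the rule. But permission to stop at a point where Section 5.4.5 says prophylaxis must continue is still a conflict, and Table 6-16 is the entry a site would consult at that visit.

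A second argument is that the 30 (+5) day visit records concomitant medications and so could reveal an early stop within the 2 months. The visit is waived only if a study visit has already taken place more than 30 days after the last dose. The stop might well be seen, but a site working from Table 6-16 would regard it as correct and have no reason to restart.

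Third, the shortfall formula only restates the 2-month floor, and the 2.0-month figure is a limiting case because a count taken at End of Study must first be reported. This is fair. The figures bound the gap for an affected subject; they do not show how many subjects are affected.

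Finally, a wording change leaves follow-up after End of Study as sparse as before. That is so. The sparse follow-up explains why an early stop would probably persist; the correction removes the instruction that allows it.

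**Conclusion.** The inconsistency is real and should be corrected. Table 6-16 permits a stop that Section 5.4.5 and Appendix 7 footnote i do not allow whenever CD4+ exceeds 200 cells/mcL less than 2 months after the last dose. For such a subject the shortfall against the minimum is more than 0 and up to 2 months (about 61 days), or 26 to 31 days in the 30 (+5) day case.

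These figures assume that the lower end of the 2 to 6 month range is the binding minimum; the 26 to 31 days also assume that End of Study coincides with the last dose. The documents give neither the usual interval from last dose to End of Study nor the share of subjects with CD4+ above 200 at that time, so the number affected cannot be estimated. No endpoint, analysis set or estimate depends on this point. It matters as a safety instruction.

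**What to change.** Reword the PJP prophylaxis entry in Table 6-16 so that prophylaxis continues for 2 to 6 months after the last dose of idelalisib **and** until CD4+ is documented above 200 cells/mcL, and may be discontinued only when both conditions are met. Footnote i already holds suitable wording.

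For consistency, add the time condition to Appendix 7 footnote j, since it is the only footnote on the End-of-Study cell.

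The cost is one table cell and one footnote, with no new visit, test or data item.
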